8. SAFETY MONITORING AND ADVERSE EVENT REPORTING

- 8.1. An adverse event (AE) is defined as any untoward medical occurrence whether thought to have been caused by the investigational medical product or the Study or not, and a Serious Adverse Event (SAE) shall mean any adverse event which is fatal, life threatening, disabling or incapacitating, requires in-patient treatment or prolongs existing hospitalization, is a congenital anomaly in the off-spring of the patient or which may require intervention to prevent the previously stated outcomes.
- 8.2. All AEs should be reported via FEARS by the health care providers. All SAEs and medical device incidents considered related to CAB-LA should be reported to GSK within 24 hours of awareness. All pregnancies associated with CAB-LA (initial notification followed by outcome of the mother and infant) should be reported to GSK within 1 week of awareness.
- 8.3. Participants will be counselled by HCPs at WVHR on the common ADEs to be aware of and when the participants should contact their HCP. Common ADEs can also be found in the FDA package insert. Participants will be counselled that If they become pregnant or suspect they might be pregnant, they should contact their HCP. All investigators and health care providers are strongly encouraged to report all pregnancies exposed to Cabotegravir to the Antiretroviral Pregnancy Registry (APR) as soon as the pregnancy is

identified. Pregnancies can be reported to the Registry at [contact] via the data forms available at www.APRegistry.com

9. HUMAN PARTICIPANTS AND DATA PROTECTION

9.1. TheraPay App

9.1.1. The TheraPay requires a username and password to access the program and data stored by the application. Only survey completed by enrolled participants will be stored within the application along with name, phone number, and email address.

10. TIMELINES

10.1. Patients will be enrolled until the n value of 105 is met.

2-3 months	3-6 months*	12 months	3 months
Development of study protocol, educational modules and survey instruments	Participant enrollment (rolling basis)	Study period	Data analysis and publication submission

13.1.5. Incentive Mapping

13.1.6. List of Tables

13.1.6.1. Study Procedures

13.1.7. List of Figures

13.1.7.1. Study Schema

13.1.7.2. Study Timelines

13.1.8. Forms for Safety Reporting

1. PROTOCOL SUMMARY

Title	A Transformative Approach Utilizing Behavioral Economics, Education, and Data Science to Support Patients Initiating PrEP with Retention-in-care and Medication Persistence
Funder	ViiV Healthcare
Study Design	Observational Cohort Study
Study Population	Patients >18 y/o who are newly started on PrEP at WVHR and have access to a smart phone with data.
Study Size	n = 105 (70 CAB-LA intervention participants and 35 oral PrEP participants)
Study Duration	12 months
Study Site(s)	West Virginia Health Right
Intervention Description	Participants will have been prescribed CAB-LA, daily FTC/TDF, or daily FTC/TAF in accordance with the WVHR standard of care by a licensed HCP prior to enrolling in the study. Those receiving CAB-LA will be in one arm and those receiving oral therapy will be in the other arm of the study.
Study Aim	To determine the persistence in injectable PrEP compared to Oral PrEP therapy
Primary Objectives	To evaluate medication persistence in patients receiving CAB-LA vs oral PrEP and who engage with a digital health companion program
Secondary Objective 1	Evaluate Retention-in-care in patients receiving CAB-LA vs oral PrEP
Secondary Objective 2	Evaluate PROs (including PrEP medication satisfaction, PrEP acceptance, stigma, and reasons for PrEP discontinuation) in patients receiving CAB-LA vs oral PrEP
Secondary Objective 3	Evaluate the acceptability, appropriateness, and helpfulness of a digital health companion program for PrEP

Secondary Objective 4	Evaluate the acceptability, barriers to, and facilitators for implementation of CAB-LA
--------------------------	--

Study Schema Figure

Figure showing study components and flow – organize by participant cohort (i.e. oral, LA, no PrEP)

Study Outcomes Table

Primary or Secondary Endpoint	Definitions	Type of Endpoint	Assessment Timepoint	Data Source	Intervention or Approach	Tool/Instrument for Endpoint
1. Primary Endpoint: PrEP adherence and Persistence	Proportion of patients reporting receipt of CAB-LA injections or use of oral PrEP at 3 months after PrEP initiation and end of study	Quantitative	M3 and end of study	Participant survey and EHR	Participant survey and EHR	Survey and Medication Retention Ratio
2. Secondary Endpoint: Retention-in-care	The proportion of patients presenting for their follow-up appointments within 30 days of their scheduled visit at months 3, 9 and 12 after PrEP initiation for the Oral PrEP arm and months 3, 9, and 11 for the CAB-LA arm.	Quantitative	M3, M9, M11, M12	Participant survey and EHR	Participant survey and EHR	Survey
3. Secondary Endpoint: PROs	PRO Set #1: PrEP Medication Satisfaction; PrEP-Related Stigma PRO Set #2: PrEP Acceptance ----- Barriers to adherence to CAB-LA injections and	Qualitative	M1, M5, M11 (PRO Set #1), M3, M9, M12 (PRO Set #2) Barriers to adherence in oral PrEP arm: M1, M2, M3, M4, M5,	Participant Survey	Patient questionnaire	Survey

	oral PrEP, and reasons for PrEP discontinuation will be assessed through brief behavioral surveys		M6, M7, M8, M9, M10, M11, M12 Barriers to adherence in CAB-LA PrEP arm: M1, M3, M5, M7, M9, M11			
4. Secondary Endpoint: Implementation Outcomes	Acceptability of Intervention Measure (AIM) and Intervention Appropriateness Measure (IAM) Health literacy evaluation and helpfulness of the education modules within the digital health program assessed through a brief survey	Qualitative	M3, M9, M12	Participant Survey	Patient questionnaire	Survey
5. Secondary Endpoint: Clinician Acceptability, Appropriateness, and Feasibility	Acceptability of Intervention Measure (AIM), Intervention Appropriateness Measure (IAM), and Feasibility of Intervention Measure (FIM)	Qualitative	M0, M6, M12, and End of Study	Clinician Survey, Interview	Clinician Survey, Interview	Clinician Survey, Interview

	Willingness to sustain provision of CAB-LA, barriers to and facilitators for provision of CAB-LA assessed through a brief survey					
--	--	--	--	--	--	--

Appendix B: CAB-LA PrEP Arm Instruments

Activity Title: Baseline Information About You

Activity Description: Today we'll ask you to answer some questions about yourself. The survey is 17 questions and should take about 10 minutes to complete.

Baseline Demographic Survey

Question	Question #
What year were you born? [Write in]	1
Which of the following best describes your racial/ethnic background? (Select all that apply) 
  African American/Black  Asian/Pacific Islander  Caucasian/White  Hispanic/Latinx  Native American/Alaska Native  A race or ethnicity not listed: [Write in] 	2
How do you describe your gender? (Select 1) 
  Female  Male  Transgender woman  Transgender man  Non-binary  A gender not listed: [Write in] 	3
How do you describe your sexual orientation? (Select 1) 
  Heterosexual/Straight  Gay or Lesbian  Bisexual  Queer or Sexually Fluid  Pansexual  A sexual orientation not listed: [Write in] 	4
What is the highest degree or school level you have completed? (Select 1) 
  Primary school  Some high school  High school diploma or GED  Some college  2-year college degree  4-year college degree  Graduate level degree  A school level not listed: [Write in] 	5
What health coverage are you currently enrolled with? (Select up to 2) 
  Medicaid  Medicare  Affordable Care Act 	6

 Uninsured  Private health insurance  A health coverage not listed: [Write in]	

Why are you using pre-exposure prophylaxis (PrEP) to prevent HIV? [Select all that apply]
  Reduce acquisition of HIV from sex  Reduce acquisition of HIV from IV drug use	7

The next 5 questions ask about your food, housing, and transportation routines from the past 12 months. If you have concerns and need support, please check in with your provider at your next visit or call 2-1-1 for immediate support.
	

In the last 12 months, was there a time when you were not able to pay the mortgage or rent on time?
  No  Yes  Not applicable	8

In the last 12 months, was there a time when you did not have a steady place to sleep or slept in a shelter (including now)?
  No  Yes	9

In the last 12 months, have you or the people you live with been unable to get utilities (heat, electricity) when it was really needed?
  No  Yes	10

Within the past 12 months, the food you bought just didn't last and you didn't have money to get more.
  Never true  Sometimes true  Often true	11

Within the past 12 months, has lack of transportation kept you from medical appointments, getting your medicines, non-medical meetings or appointments, work, or from getting things that you need?
  No  Yes	12

Do you feel physically and emotionally safe where you currently live?
  Yes  No	13

During the past 30 days, have you used any of the following?
 
 • An illegal drug (such as by snorting it or injecting it) • Pain killer to get high (like OxyContin, sometimes called Oxy or OC) or Percocet (sometimes called Percs) • Prescription drugs not prescribed to you  No  Yes	14

People who experience discrimination may be at higher risk of negative health outcomes. Sharing your experiences with discrimination in everyday life and in healthcare settings may help researchers learn how to reduce negative health outcomes associated with discrimination.
	

The next 3 statements describe how others may treat you.	
In your day-to-day life, how often do any of these happen to you?	
You are treated with less respect than other people are. 
  Never  Less than once a year  A few times a year  A few times a month  At least once a week  Almost every day 	15
People act as if they're better than you. 
  Never  Less than once a year  A few times a year  A few times a month  At least once a week  Almost every day 	16
What do you think is the main reason for these experiences? (Select 1) 
  Your gender  Your sexual orientation  Your race  Your religion  Some aspect of your physical appearance  Your education or income level  Other: [Write in] 	17

End Message: Thank you for completing this survey!

Persistence Assessment

Activity Title: Are You Still Taking PrEP?

Activity Description: In this short survey, we'll ask you some questions about your PrEP journey and any challenges you may have encountered.

Activity:

1. Are you still getting PrEP medicine by an injection from your healthcare provider?

- Yes, I am taking PrEP ([branching logic to question 4](#))
- No, I stopped taking PrEP ([branching logic to question 2](#))

2. If you stopped taking PrEP, which of the following best describes the reason(s) why?

[Select up to 2]

- I no longer feel I needed to take PrEP ([branching logic to question 3 if selected](#))
- It was too difficult to take to take PrEP as prescribed with my lifestyle
- I felt I was being judged by others for taking PrEP
- I experienced side effects from taking PrEP

- I take too many medications
- There were too many appointments as part of my PrEP care
- I tested positive for HIV
- Other: [Fill in the blank]

3. Which of the following best describes why you no longer feel you need to take PrEP?

- I am no longer having sex
- I am in a monogamous relationship
- I am no longer using injectable drugs
- My partners and I are all regularly using condoms and getting tested for HIV
- Other: [Fill in the blank]

4. If you are still taking PrEP, what challenges have you experienced?

- Have not experienced any challenges
- Keeping up with clinical visits and laboratory testing
- Concerns about side effects
- Finding transportation to my appointments
- Stigma or discrimination from family, friends, or partner(s)
- Stigma or discrimination from healthcare professionals
- Other: [Fill in the blank]

5. Did a healthcare provider (for example, a doctor, nurse or pharmacist) or navigator ever ask you what may make it difficult for you to take PrEP? (Month 1 & 11)

- Yes
- No
- Unsure

Activity Type: Patient Reported Outcomes – Set 1

Activity Title: Your Experiences With PrEP

Activity Description: This month we'll ask you to answer questions about your experience using PrEP and your thoughts about PrEP-related stigma. We'll also ask some questions about your experience using this mobile app to support you taking PrEP. The survey is 3 parts with a total of 24 questions. It should take you 10-15 minutes to complete.

Activity:

Part 1. Tell us about your experience using PrEP

The following questions are related to the PrEP medicine you use to protect you from HIV infection and your experience over the **past 4 weeks**. Please answer each question by selecting a number on each of the scales.

1. How satisfied are you with your **current medicine** for PrEP?
 - Very satisfied
 - Satisfied

- Neither satisfied or dissatisfied
 - Dissatisfied
 - Very dissatisfied
2. How **bothered** are you by **any side effects** from the medicine you use for PrEP?
- Very unbothered
 - Unbothered
 - Neither unbothered or bothered
 - Bothered
 - Very bothered
 - I have not experienced any side effects in the last 4 weeks
3. How satisfied are you with the **convenience** of PrEP recently?
- Very satisfied
 - Satisfied
 - Neither satisfied or dissatisfied
 - Dissatisfied
 - Very dissatisfied
4. How satisfied are you with the **discreetness** of PrEP recently?
- Very satisfied
 - Satisfied
 - Neither satisfied or dissatisfied
 - Dissatisfied
 - Very dissatisfied
5. How satisfied are you with your **understanding of using PrEP** to prevent HIV?
- Very satisfied
 - Satisfied
 - Neither satisfied or dissatisfied
 - Dissatisfied
 - Very dissatisfied
6. How satisfied are you with the extent to which PrEP **fits in with your lifestyle**?
- Very satisfied
 - Satisfied
 - Neither satisfied or dissatisfied
 - Dissatisfied
 - Very dissatisfied
7. Would you recommend this type of PrEP to someone else who wants to protect themselves from HIV?

- Yes, I would **definitely recommend** this type of PrEP
- Yes, I would **recommend** this type of PrEP
- Not sure if I would recommend or not recommend this type of PrEP
- No, I would **not recommend** this type of PrEP
- No, I would **definitely not recommend** this type of PrEP

8. How satisfied would you be to continue your present form of PrEP?

- Very satisfied
- Satisfied
- Neither satisfied or dissatisfied
- Dissatisfied
- Very dissatisfied

Part 2. What are your thoughts about PrEP-related stigma?

Stigma is a negative and unfair belief about someone because of a particular characteristic or attribute. Please answer the following statements to the best of your ability.

Indicate how much you agree with the following:

	Completely agree	Agree	Neither agree or disagree	Disagree	Completely disagree
I feel ashamed to go to the doctor for PrEP injections/shots.	()	()	()	()	()
People experience negative judgment because they take PrEP.	()	()	()	()	()
Someone using PrEP should keep their PrEP injection appointments hidden.	()	()	()	()	()

	Completely agree	Agree	Neither agree or disagree	Disagree	Completely disagree
Someone taking PrEP would be seen by others as slutty.	()	()	()	()	()

People taking PrEP receive praise for being responsible.	()	()	()	()	()
My friends would be supportive of me taking PrEP.	()	()	()	()	()

	Completely agree	Agree	Neither agree or disagree	Disagree	Completely disagree
Someone taking PrEP would be treated unfairly by their doctors.	()	()	()	()	()
People experience problems when they tell their sex partner(s) they are taking PrEP.	()	()	()	()	()
I feel proud to take PrEP.	()	()	()	()	()

	Completely agree	Agree	Neither agree or disagree	Disagree	Completely disagree
People on PrEP are taking care of their health.	()	()	()	()	()
My family would be supportive of me taking PrEP.	()	()	()	()	()

Part 3. What is your experience using the TheraPay mobile app?

Please assess your experience using the TheraPay mobile app to support you in your journey using PrEP.

	Completely agree	Agree	Neither agree nor disagree	Disagree	Completely disagree
1. The TheraPay mobile app meets my approval.	1	2	3	4	5
2. The TheraPay mobile app is appealing to me.	1	2	3	4	5
3. I like the TheraPay mobile app.	1	2	3	4	5
4. I welcome the TheraPay mobile app.	1	2	3	4	5

End Message: Thank you for completing this survey! We will ask you these same questions again later to see how your responses have changed.

Patient Reported Outcomes – Set 2

Activity Title: Your Experiences With PrEP

Activity Description: This month we'll ask you to answer questions about your experience using PrEP (pre-exposure prophylaxis). We'll also ask some questions about your experience using this mobile app to support you taking PrEP. The survey is two parts with a total of 16 questions. It should take you 8-12 minutes to complete.

Part 1. Tell us about your experience using PrEP

Question	Question # CAB LA Arm [14]	Sub-concept
Over the past 4 weeks, how confident were you that PrEP prevented you from acquiring HIV ?  Very confident  Quite confident  Somewhat confident  A little confident  Not at all confident	1	Perceived efficacy
[CAB-LA arm] Over the past 4 weeks, did you experience any side effects, including injection site side effects (such as redness, bruising, or swelling) from the PrEP injection?  No (branching logic to question 5)  Yes (branching logic to show 3)	2	Acceptance of side effects
Over the past 4 weeks, how acceptable or unacceptable did you find the side effects from PrEP?  Very acceptable  Acceptable  Neither acceptable or unacceptable  Unacceptable  Very unacceptable	3 (branching logic)	Acceptance of side effects
Over the past 4 weeks, did the side effects of the PrEP medication interfere with your physical activity (such as lifting things, walking, jogging), your leisure or free time activities (such as gardening, reading, dancing, visiting friends), or your daily activities (such as shopping, working, house work, yard work)?  No, not at all  Yes, a little  Yes, somewhat  Yes, quite a bit  Yes, very much	4 (branching logic)	Acceptance of side effects
[CAB LA arm] Over the past 4 weeks, did you experience any pain when getting your PrEP injection?	5	Acceptance of side effects

 No (branching logic to question 7)  Yes (branching logic to question 6)		

[CAB LA arm] Over the past 4 weeks, how acceptable or unacceptable did you find the pain you experienced when getting your PrEP injection?
  Very acceptable  Acceptable  Neither acceptable or unacceptable  Unacceptable  Very unacceptable	6 (branching logic)	Acceptance of side effects

[CAB LA arm] Over the past 4 weeks, how acceptable or unacceptable did you find the time it took to get the PrEP injection at your doctor's office?
  Very acceptable  Acceptable  Neither acceptable or unacceptable  Unacceptable  Very unacceptable	7	Convenience

[CAB LA arm] Over the past 4 weeks, how acceptable or unacceptable did you find the number of times you had to get your PrEP injection?
  Very acceptable  Acceptable  Neither acceptable or unacceptable  Unacceptable  Very unacceptable	8	Convenience

[CAB LA arm] Over the past 4 weeks, how easy or difficult was it to remember to go to your appointments for your PrEP injection?
  Very easy  Easy  Neither easy or difficult  Difficult  Very difficult	9	Convenience

[CAB LA arm] Over the past 4 weeks, how easy or difficult was it to fit in getting the PrEP injection into your daily life?
 
  Very easy  Easy  Neither easy or difficult  Difficult  Very difficult 	10	Convenience

Over the past 4 weeks, did you ever feel like you needed to hide your attendance to PrEP injection appointments so others would not see you?
 
  No, not at all  Yes, occasionally  Yes, often  Yes, quite often  Yes, all the time 	11	Convenience

Over the past 4 weeks, how convenient or inconvenient did you find taking the PrEP?
 
  Very convenient  Convenient  Neither convenient or inconvenient  Inconvenient  Very inconvenient 	12	Convenience

[CAB LA arm] In the future, would you choose to continue using the PrEP injection to protect yourself from HIV infection?
 
  Yes definitely  Yes probably  I don't know  Probably not  Definitely not 	13	Overall Acceptance

[CAB LA arm] In the future, would you choose to switch to using the PrEP pill to protect yourself from HIV infection?
 
  Definitely not  Probably not  I don't know  Yes, probably  Yes, definitely 	14	Overall Acceptance

Thinking about all aspects of using PrEP over the past 4 weeks, how acceptable or unacceptable did you find the medicine?
 
  Very acceptable  Acceptable  Neither acceptable or unacceptable  Unacceptable  Very unacceptable 	15	Overall Acceptance

Overall, over the past 4 weeks, how acceptable or unacceptable did you find taking all of your medicines, including PrEP and any other pills, tablets, or injections ?		
 Very acceptable  Acceptable  Neither acceptable or unacceptable  Unacceptable  Very unacceptable	16	Overall Acceptance

Part 2. What is your experience using this mobile app?

Please assess how **appropriate** the use of a mobile app has been to support you in your journey using PrEP.

	Completely agree	Agree	Neither agree nor disagree	Disagree	Completely disagree
1. Using a mobile app to support me using PrEP seems fitting.	1	2	3	4	5
2. Using a mobile app to support me using PrEP seems suitable.	1	2	3	4	5
3. Using a mobile app seems applicable.	1	2	3	4	5
4. Using a mobile app to support me using PrEP seems like a good match.	1	2	3	4	5

[figure not shown]
End Message: Thank you for completing this survey! We will ask you these same questions again later to see how your responses have changed.

Health Literacy Evaluation - Month 2

Activity Description: Was the pop quiz on PrEP medicine helpful? What did you learn?

Activity:

1. How helpful was the pop quiz reviewing important facts about PrEP?

2. True/False: A person who takes PrEP will also need to use condoms to prevent other STIs.

[figure not shown]
- **True**
 - That's correct! PrEP only protects against HIV. Condoms will protect you against other sexually transmitted infections, such as syphilis, gonorrhea, or chlamydia. Condoms will also protect against unintended pregnancy.
- **False**
 - Not quite. PrEP only protects against HIV. Condoms will protect you against other sexually transmitted infections, such as syphilis, gonorrhea, or chlamydia. Condoms will also protect against unintended pregnancy.

Health Literacy Evaluation – Month 4

Activity Description: Was the video on protecting yourself helpful? What did you learn?

Activity:

1. How helpful was the video on sexual health, safer IV drug use, and protecting yourself?

2. **True/False: All body parts used for sex should be tested for HIV & sexually transmitted infections (STIs).**

- **True**

That's correct! In many cases, this means you should have three body parts tested – (1) the throat; (2) the front (vagina, front hole, penis, urethra); and (3) the back (anus and rectum).
- **False**

Not quite. All body parts used for sex should be tested for STIs. In many cases, this means you should have three body parts tested – (1) the throat; (2) the front (vagina, front hole, penis, urethra); and (3) the butt hole and rectum.

3. **True/False: All sexually transmitted infections (STIs) will cause symptoms.**

- a. **True**

Not quite. Many STIs do not cause any symptoms that you would notice. It is important to get regular testing.
- b. **False**

That's correct! Many STIs do not cause any symptoms that you would notice. It is important to get regular testing.

Health Literacy Evaluation – Month 6

Activity Description: Was the video on “Building a Support System for HIV Prevention” helpful? What did you learn?

Activity:

1. How helpful was the video on building your support system?

2. True/False: West Virginia Health Right has services available if you are facing stressors or challenges.

True

That’s right! There are many services available including telehealth appointments, health education classes, support for alcohol or drug addiction, LGBTQIA+ health, help from social workers, family planning services, dental and vision care, primary health care, behavioral or mental health care, pharmacy, and testing and screening for different health concerns. You can contact WVHR at [contact] for more information.

False

Not quite. There are many services available including telehealth appointments, health education classes, support for alcohol or drug addiction, LGBTQIA+ health, help from social workers, family planning services, dental and vision care, primary health care, behavioral or mental health care, pharmacy, and testing and screening for different health concerns. You can contact WVHR at [contact] for more information.

3. True/False: A support person could be a partner, family member, friend, peer navigator, or social worker.

True

That’s correct. Any one of these people could help support you. It’s your choice and completely up to you who you want to bring on your support team.

False

Not quite. Any one of these people could help support you. It’s your choice and completely up to you who you want to bring on your support team.

Health Literacy Evaluation – Month 8

Activity Description: Was the article on “Being an Active Participant in Your Own Care” helpful? What did you learn?

Activity:

1. How helpful was the article on being an active participant in your own care?

2. Which of the following best describes shared decision-making?

- When your doctor makes a decision about your healthcare that they feel is in your best interest**

Not quite. Shared decision-making is a process where you and your healthcare providers work together to make decisions that reflect what's most important to you while making sure your medications are safe and effective.

- When you and your doctor work together to make a decision about your healthcare that considers your values, goals and concerns**

That's right! Shared decision-making is a process where you and your healthcare providers work together to make decisions that reflect what's most important to you while making sure your medications are safe and effective.

- When your doctor works with another member of the care team (such as a nurse or social worker) to make a decision about your healthcare**

Not quite. Shared decision-making is a process where you and your healthcare providers work together to make decisions that reflect what's most important to you while making sure your medications are safe and effective.

3. **True/False: Asking questions during your appointments is an important part of shared decision-making.**

- True**

That's right! By asking your healthcare provider questions, you can get all of the information you need to make decisions about your health.

- False**

[figure not shown]
Not quite. By asking your healthcare provider questions, you can get all of the information you need to make decisions about your health.

Health Literacy Evaluation – Month 8

Activity Description: Was the video on “Overcoming Stigma and Becoming a Health Advocate” helpful? What did you learn?

Activity:

1. How helpful was the video on overcoming stigma and becoming a health advocate?

2. True/False: Stigma is when someone views a person or themselves in a negative way because of their unique identity, circumstances, and/or experiences.

True

That's right! Stigma is a negative and unfair belief about someone because of a particular characteristic or attribute.

False

Not quite. Stigma is a negative and unfair belief about someone because of a particular characteristic or attribute.

3. True/False: Sharing your experience with PrEP can help fight stigma surrounding it.

True

That's right! Calling out biases and finding support within a community can help break the stigma cycle.

False

Not quite. Calling out biases and finding support within a community can help break the stigma cycle.

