6.2.3. Persistence Assessment CAB-LA

6.2.3.1. The proportion of participants who received at least one PrEP injection who remained on injectable PrEP or oral bridging at months 3 and 11 measured by the self-report assessment and validated with claims data.

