6.5. Switching between PrEP regimens

6.5.1. To be included in final data analysis, participants cannot switch between PrEP regimens before 6-months duration of initial PrEP.

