6.14. STATISTICAL ANALYSIS

6.14.1. Study Endpoints

6.14.1.1. Medication Adherence and Persistence

Medication persistence is defined as continuing to take PrEP over time independent of adherence to the medication regimen. The proportion of

patients reporting receipt of CAB-LA or oral PrEP at months 3 (early) and end of study (late) will be measured through patient questionnaires and validation protocols. Medication adherence is defined as taking PrEP in line with medical advice.

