You are treated with less respect than other people are. 
  Never  Less than once a year  A few times a year  A few times a month  At least once a week  Almost every day 	15
People act as if they're better than you. 
  Never  Less than once a year  A few times a year  A few times a month  At least once a week  Almost every day 	16
What do you think is the main reason for these experiences? (Select 1) 
  Your gender  Your sexual orientation  Your race  Your religion  Some aspect of your physical appearance  Your education or income level  Other: [Write in] 	17

End Message: Thank you for completing this survey!

Persistence Assessment

Activity Title: Are You Still Taking PrEP?

Activity Description: In this short survey, we'll ask you some questions about your PrEP journey and any challenges you may have encountered.

Activity:

1. Are you still taking PrEP medicine by mouth?

- Yes, I am taking PrEP (branching logic to question 4)
- No, I stopped taking PrEP (branching logic to questions 2)

2. Over the past week, how many days did you miss taking PrEP?

- 0
- 1
- 2
- 3
- 4
- 5
- 6

7

3. If you stopped taking PrEP, which of the following best describes the reason(s) why? [Select up to 2]

- I no longer feel I needed to take PrEP (branching logic to question 3 if selected)
- It was too difficult to take PrEP with my schedule
- I did not want people to know I was taking it or I felt I was being judged by others for taking PrEP
- I did not like the side effects
- I take too many medications
- There were too many appointments as part of my PrEP care
- I tested positive for HIV
- Other: [Fill in the blank]

4. Which of the following best describes why you no longer feel you need to take PrEP?

- I am no longer having sex
- I am in a monogamous relationship
- I am no longer using injectable drugs
- My partners and I are all regularly using condoms and getting tested for HIV
- Other: [Fill in the blank]

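### The persistence forms cannot record oral bridging or a regimen switch, and 6.2.3.1 and Section 7 disagree on bridging, so a bridging CAB-LA participant can be scored either way

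*Combined protocol and SAP*

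**What the plan says.** In Appendix B, Q1 of the CAB-LA persistence assessment reads "Are you still getting PrEP medicine by an injection from your healthcare provider". In Appendix C, the oral form asks "Are you still taking PrEP medicine by mouth". Each has two answers: a Yes stating that the participant is taking PrEP, and "No, I stopped taking PrEP". A No leads to the reasons for stopping (on the oral form, after a missed-days item). Neither list of reasons has an option for having changed to another form of PrEP. Both end in a free-text Other.

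The definitions that this item serves are not the same throughout:

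- Section 6.2.3.1 counts CAB-LA participants "who remained on injectable PrEP or oral bridging at months 3 and 11 measured by the self-report assessment and validated with claims data".
- Section 6.2.4.1 counts those who started oral PrEP and are still on oral PrEP at months 3 and 12, again by self-report validated with claims.
- Section 7 compares continued injections in the CAB-LA cohort with continued PrEP by mouth in the oral cohort, as reported on the persistence assessment. It does not mention bridging.
- Section 6.14.1.1 is more general: "Medication persistence is defined as continuing to take PrEP over time independent of adherence to the medication regimen". Section 6.2.2.1 is similar. Both can be read as any PrEP.

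On switching, 6.5.1 says that, to be in the final analysis, "participants cannot switch between PrEP regimens before 6-months duration of initial PrEP". Section 7 adds that self-reported persistence is validated by the medication possession ratio (MPR).

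**The concern.** A participant who is on PrEP, but not by the route named in the stem, has no true answer. Yes is false for the question, and No is false for the answer text. The plan expects such participants. The CAB-LA adherence assessment in 6.2.6.1 allows for oral bridging while off injections, and exclusion 5.2.5 covers only bridging before injectable PrEP. Section 6.5.1 keeps those who switch after six months.

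Persistence is a co-primary endpoint, and this item is its self-report measure. If participants in the same situation answer differently, the endpoint partly reflects how they read the sentence. A No also sends people who are still on PrEP to the stopping-reasons item, which feeds the secondary outcome on reasons for discontinuation.

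**Working it through.** **Step 1: score each answer under each definition.** For each type of participant, the table shows whether the recorded answer gives the class that the text intends.

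| Participant | Q1 answer | 6.2.3.1 / 6.2.4.1 | Section 7 | Any-PrEP reading of 6.2.2.1 / 6.14.1.1 |
|---|---|---|---|---|
| CAB-LA, on oral bridging | Yes | right | wrong | right |
| CAB-LA, on oral bridging | No | wrong | right | wrong |
| Either arm, switched after month 6 | Yes | wrong | wrong | right |
| Either arm, switched after month 6 | No | right | right | wrong |

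Bridging is the clear case, because the two operational definitions themselves disagree and the form does not collect what is needed to apply 6.2.3.1. For switchers, 6.2.3.1, 6.2.4.1 and Section 7 agree with each other, and the conflict is only with the general wording.

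**Step 2: timing.** Section 6.5.1 removes those who switch before six months, so switching can affect only the end-of-study comparison. Bridging can affect month 3 as well.

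**Step 3: size of one answer.** CAB-LA arm: 1/70 = 1.4 points. Oral arm: 1/35 = 2.9 points.

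**Step 4: reproduce the plan's interval.** Inputs from Section 7, Sample Size: .90 with n = 70 and .65 with n = 35, stated for adherence. Unpooled Wald interval: SE = √(.90×.10/70 + .65×.35/35) = .0882. Then .25 ± 1.96 × .0882 = .0771 to .4229, the plan's figure.

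**Step 5: illustration for bridging.** Assumption: true persistence under 6.2.3.1 equals those adherence inputs, that is 63/70 and .65. Let k of the 63 be on bridging and answer No. CAB-LA persistence is then recorded as (63 − k)/70. Fisher's test uses 23/35 for the oral arm (.65 × 35 = 22.75, rounded).

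| k (share of arm) | CAB-LA recorded | 95% interval for difference | Fisher p |
|---|---|---|---|
| 0 | .900 | .0771 to .4229 | .006 |
| 1 (1.4%) | .886 | .0610 to .4104 | .008 |
| 2 (2.9%) | .871 | .0450 to .3978 | .018 |
| 4 (5.7%) | .843 | .0133 to .3724 | .044 |
| 5 (7.1%) | .829 | -.0024 to .3596 | .083 |
| 7 (10.0%) | .800 | -.0337 to .3337 | .150 |

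Section 7 allows either chi-square or Fisher's test. The chi-square test without continuity correction gives .049 at k = 5 and .075 at k = 6, so the exact crossing point depends on the test.

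**Step 6: illustration for switchers, any-PrEP reading only.** Hold CAB-LA at .90 and let m oral-arm participants now on injections answer No. Counting them as persistent gives .65 + m/35 in the oral arm. At m = 3 the interval is .0022 to .3264, and at m = 4 it is -.0215 to .2929.

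**The case against.** The strongest reply is that the form is not the only evidence. Self-report is to be validated with claims and MPR, the outcomes table names the EHR as a source beside the survey, and 5.1.3 requires dispensing by the WVHR pharmacy. Those records should show a switch or bridging supply, and they, not the form, can be used to apply 6.5.1. A switch can also be written under Other. This stands in part: misscoring is a risk, not a certainty. However, the plan does not say which source decides when they disagree, or whether bridging pills count towards MPR. Other reaches only those who answer No, and no rule recodes Q1 from it.

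A reader might also infer that the form misclassifies everyone who switches and so biases the co-primary comparison in both arms by a known amount. The documents do not support that:

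- A switcher who answers No is correctly non-persistent under 6.2.3.1, 6.2.4.1 and Section 7, which fits the stated aim of comparing persistence on injectable and oral PrEP.
- Those who switch early are excluded.
- Bridging concerns the CAB-LA form only.
- No rate or direction of switching is given, so any assumed percentage, and any claim about balance between arms, comes from outside the plan.
- The 25-point difference and its interval are for adherence. The plan states no persistence assumption.

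**Conclusion.** The point holds as a fault of item wording and endpoint definition. In the CAB-LA arm, 6.2.3.1 relies on a self-report that cannot record bridging, and Section 7 applies a different rule, so the same participant can be scored either way. In both arms, a switch after month 6 has no structured answer. Its scoring is settled under the regimen-specific definitions only if the participant answers No, and that No sends someone still on PrEP to the stopping-reasons item.

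The firm size is 1.4 points per misscored CAB-LA answer and 2.9 points per misscored oral answer. The illustrations show that a handful of answers could matter in a study of 105. They rest on borrowed adherence inputs and on assumed counts, and they do not estimate bias. The item and definitions should be changed. The fault does not by itself invalidate the comparison.

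**What to change.** 1. Reconcile 6.2.2.1, 6.2.3.1, 6.2.4.1, 6.14.1.1 and Section 7 into one regimen-persistence definition that says whether bridging counts. Report any-PrEP persistence beside it.
2. Replace the Q1 answers with: still on the PrEP I started; temporarily on pills between injections (CAB-LA form only); changed to a different form of PrEP, with date and reason; not taking any PrEP. Send only the last to the stopping-reasons item.
3. State that WVHR dispensing and injection records decide when they disagree with self-report, and that they are used to apply 6.5.1.

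The definitions must come first, because rewording Q1 alone would leave the scoring of bridging open. The cost is a slightly longer item in two app forms, edits to the sections named, and recoding from pharmacy records of any responses already collected. No visit or staff is added.
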